 9. Shape Matching Task. The shape matching task assesses cognitive control, or resistance to distraction. Individuals are presented with probe and target shapes and must decide whether they are the same shape. On some trials a distractor shape will be present, which the individual is instructed to ignore. (approximately 25 minutes)

Module 14 (Group B) or 1 Month (Group A) – Online

- Both groups will receive a personalized survey link via Qualtrics.

1. FFMQ non-reactivity (approximately 1 minute)
2. PSWQ (approximately 3 minutes)
3. MAIA (approximately 5 minutes)
4. PROMIS Sleep & Anxiety (approximately 1 minute)
5. WIS (approximately 1 minute)
6. GAD-7 (approximately 2 minutes)

Module 30 (Group B) or 2 Months (Group A)

- Group A will complete the first five items using a personalized survey link via Qualtrics and the sixth, the GAD-7, will be completed as part of the Unwinding Anxiety assessment.
- Group B will complete the first seven items using a personalized survey link via Qualtrics
- Both groups will complete the shape matching task on a study laptop.
 1. FFMQ non-reactivity (approximately 1 minute)
 2. PSWQ (approximately 3 minutes)
 3. MAIA (approximately 5 minutes)
 4. PROMIS Sleep & Anxiety (approximately 1 minute)
 5. WIS (approximately 1 minute)
 6. GAD-7 (approximately 2 minutes)
 7. Net promoter score (approximately 1 minute)
 8. Shape matching task (approximately 25 minutes)

2 Months post-intervention (Group B) or 4 Months (Group A)

- Both groups will complete the first six items using a personalized survey link via Qualtrics and the shape matching task will be completed on a study laptop.
 1. FFMQ non-reactivity (approximately 1 minute)
 2. PSWQ (approximately 3 minutes)
 3. MAIA (approximately 5 minutes)
 4. PROMIS Sleep & Anxiety (approximately 1 minute)

5. WIS (approximately 1 minute)
6. GAD-7 (approximately 2 minutes)
7. Shape matching task (approximately 25 minutes)

4. Participant Population.

Description of participant population:

We will recruit people who experience sleep disturbances related to anxiety in order to address Aims 1 & 2 of this study. We will recruit people who live within a 30-minute drive of Providence, RI because people who live within close proximity to Providence are more likely to return for follow-up visits and complete the study.

Participants will meet the following criteria:

Inclusion:

1. 18 years or older
2. PSWQ > 40 based on established cut-off suggesting GAD

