3. $\geq 5/10$ on Worry Interfering with Sleep scale (WIS)
4. Able to read and speak English, because the Unwinding Anxiety app is available in English only.
5. Owns a smartphone (UA app can only be used on a smartphone)
6. Willingness to wear the Fitbit Inspire tracker

Exclusion:

1. If using psychotropic medication - not on a stable dosage for at least 6 weeks
2. Medical disorder of the severity that would interfere with ability to participate (e.g. cancer, multiple sclerosis, Parkinson's disease, ALS, etc. These disorders impact sleep quality which could confound study outcomes.)
3. As needed (i.e. prn) benzodiazepine or hypnotic sleep aid
4. Known sleep disorder (e.g. obstructive sleep apnea, restless leg syndrome – because these disorders impact sleep quality.)
5. Psychotic disorder (Mindfulness meditation has to be carefully monitored with people experiencing psychosis. We are not able to provide this type of monitoring given budget constraints.)
6. Post-Traumatic Stress Disorder (Mindfulness meditation has to be carefully monitored with people experiencing PTSD. We are not able to provide this type of monitoring given budget constraints.)
7. Severe Depression (PHQ-2 score > 3) (People experiencing severe depression may also experience sleep disorders which could confound study outcomes.)
8. Current shift work employment (People working alternate shifts may have sleep quality problems which could confound study outcomes.)
9. BMI > 30. (People who are obese may have sleep quality problems which could confound study outcomes.)
10. Evening caffeine use (Caffeine use late in the day can impact the quality of a person's sleep, hence the possibility of confounding study outcomes.)
11. Pregnancy (Women in various stages of pregnancy often have sleep quality problems, hence the possibility of confounding study outcomes.)
12. New parents whose child is not sleeping through the night (New parents are often awakened every 3 – 4 hours by a newborn which could confound study outcomes)
13. Lives in same household as someone already enrolled in this study (To prevent study participants from sharing study information with one another.)

Participant enrollment target:

Our goal is to collect 64 complete and usable data sets, so our plan is recruit and enroll 80 participants.

Enrolling 80 participants will be sufficient to cover any participants who don't complete the study and it will allow us to meet our N of 64.

Check-ins

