Analyses will be conducted in R using an intent-to-treat approach (ITT). Fischer's exact tests for categorical and Kruskal Wallis tests for continuous variables will be used to determine any between-group differences in baseline demographics. To examine between-group differences in behavioral outcome measures at the primary endpoint (2 months), Welch's t-tests will be used along with Mann Whitney U tests for data that violates the assumption of normality. A series of Generalized Estimating Equations (GEE) will be used to estimate the adjusted intervention effect by regressing change in outcomes at each follow-up on time, group, time*group and confounders identified a priori (using correlation analysis. GEE's are used for longitudinal data in order to account for within-subject covariance over time. False Discovery Rate will be used to correct for multiple comparisons.

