Sleep period time (SPT) will be calculated from the paper sleep diaries (PSDs) by subtracting self-reported bedtime from wake time. Fitbit recorded bedtime, wake time, number of sleep minutes, and number of awake minutes will be used to calculate estimated TST and sleep efficiency (SE). To improve reliability, average estimated TST will only be calculated for participants with ≥ 3 days recorded during each wear period. Analysis will utilize the same approach as described for the behavioral measures with the addition of a complete case (CC) approach; participants who did not complete the baseline wear period will be excluded from analysis. For the ITT analysis, we will compare the robustness of our findings using two statistical approaches for handling missing data. First, we will use inverse probability weighting with propensity scores. This is a two-step method: 1) using logistic regression, the probability of missingness is modeled as a function of baseline covariates and baseline values of the outcome and 2) the inverse of the propensity scores (predicted probabilities of dropout from the first step) serve as weights in our regression model of the outcomes. Provided the data is missing at random (MAR) or that the probability of missingness can be fully explained by observable data, this approach produces asymptotically unbiased estimates. To allow for the possibility that the MAR assumption may not hold, we will also use a second approach, pattern mixture models, in which the distribution of the outcome is assumed to follow a mixture of two distributions: one for those who complete follow up and another for those who do not. We will subsequently examine effects under a per-protocol analysis.

Mediation analyses will be conducted using both the Baron and Kenny four-step approach in addition to causal mediation models. In the causal mediation analysis, we will focus on the natural direct and indirect effects and use the bootstrap method with 1,000 bootstrapped resamples to compute the standard errors and 95% confidence interval.

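### The test tied to the 2-month primary endpoint is an available-case comparison under an ITT label; the SAP leaves open whether its missing-data methods cover that comparison and which 2-month result decides

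*Combined protocol and SAP*

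**What the plan says.** The first paragraph of the Statistical Analysis Plan opens with "Analyses will be conducted in R using an intent-to-treat approach (ITT". For the behavioural measures it sets the purpose, "To examine between-group differences in behavioral outcome measures at the primary endpoint (2 months", and states that "Welch's t-tests will be used along with Mann Whitney U tests for data that violates the assumption of normality". It gives no rule for a participant who has no 2-month score. The same paragraph then adds GEE models, "regressing change in outcomes at each follow-up on time, group, time*group and confounders identified a priori", so the 2-month contrast is estimated a second time. Neither analysis is ranked above the other, and no single outcome is named as primary.

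Missing data appear only in the second paragraph, which opens with sleep diary and Fitbit measures: "For the ITT analysis, we will compare the robustness of our findings using two statistical approaches for handling missing data". The first approach is inverse probability weighting. Its missingness model uses only baseline information, and the results "serve as weights in our regression model of the outcomes". The second is pattern mixture models, with no statement of which analysis they modify.

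Three design features bear on who will have a 2-month score:
- Under Participant enrollment target, the aim is 64 complete data sets, and "our plan is recruit and enroll 80 participants".
- Under Procedures, the visit that supplies the 2-month score is set by Module 30 in Group B and by 2 months in Group A. Group A receives the app only on completing that visit.
- An online assessment comes before it (Module 14 in Group B, 1 month in Group A), for which "Both groups will receive a personalized survey link via Qualtrics".

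**The concern.** A two-sample test can use only people who have the score being compared. For this test, ITT can therefore mean no more than that participants are analysed in their assigned groups; it does not mean that everyone randomised is included. The scores already collected at baseline and at the online assessment say something about how people lost before the third visit were doing, and the test discards them.

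Unequal loss between arms is plausible. A Group B participant reaches the visit by progressing through the app, whereas a Group A participant has an incentive to attend because the app follows. If Group B participants who are doing poorly are the ones who leave, the remaining Group B scores look better than those of the whole arm, and the comparison tilts towards the app. If the Welch and GEE results then differ, the plan gives no way to choose between them.

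**Working it through.** **1. The plan's own figure.** Implied loss = 1 − 64/80 = 0.20, and 64/(1 − 0.20) = 80, so the enrolment figure is consistent. The 20% is back-calculated, not stated. No alpha, power, effect size or SD is given, so the 64 itself cannot be derived. The allowance is 80 − 64 = 16 incomplete data sets; missing 2-month scores could be fewer, because a data set may be incomplete for other reasons.

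**2. What the test would use.** Assuming 1:1 allocation (the ratio is not stated), 20% loss leaves about 32 v 32 of 40 v 40. With two-sided alpha 0.05 and 80% power (both assumed), the detectable difference is (1.960 + 0.842) × √(2/n): 0.70 SD at n = 32 and 0.63 SD at n = 40.

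**3. Completer effect against all-randomised effect.** Suppose Group B participants without a score have the Group A mean, and Group A loss is non-informative. The all-randomised effect is then the completer effect times (40 − m)/40, where m is the number missing in Group B. This gives 1.0 for m = 0, 0.8 for m = 8 and 0.6 for m = 16.

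**4. Simulated bias with no true effect.** Each scenario has 4,000 trials and 40 per arm. Negative values favour the app. In the last three rows, Group A loss is random. All correlations and loss patterns are assumed.

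| Loss pattern | Welch bias | Rejection at 5% |
|---|---|---|
| About 20%, unrelated to severity in both arms | about 0.00 SD | 4.9% |
| 20% per arm, equally tied to severity (log-odds 0.8 and 1.2 per SD) | 0.00 SD | 5.1% to 5.8% |
| Group B loss (about 20%) tied to baseline score, correlation 0.6 | −0.12 SD | 7.5% |
| Group B loss (about 20%) tied to the 2-month score, correlation 0.6 | −0.19 SD | 11.9% |
| Group B loss (20% to 37%) tied to 1-month score (log-odds 0.8 to 1.2 per SD), correlation 0.7, Group A loss 5% to 20% | −0.11 to −0.25 SD | 7.6% to 17.1% |

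The last row can be read by hand. When loss depends only on the 1-month score, bias = 0.7 × (1-month mean of Group B completers minus that of all Group B). The range therefore corresponds to completers who are 0.11/0.7 = 0.16 to 0.25/0.7 = 0.36 SD better at 1 month than the whole arm. The upper end needs about 37% loss in Group B, which is 0.37 × 40 ≈ 15 people, or nearly the whole allowance of 16 in one arm. With a true effect of 0.50 SD, Welch averages 0.61 to 0.75 in these scenarios.

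**5. What a model recovers.** In the last-row scenarios, a likelihood estimate using baseline and 1-month scores stays within 0.011 SD of zero under no effect. It averages 0.50 under a true 0.50, with a standard error of 0.24 to 0.26, about the same as Welch. That result assumes every dropout has a 1-month score. If dropouts lack it, the bias is −0.03 to −0.09 SD; if loss depends on the unseen 2-month score, it is −0.06 to −0.07 SD. Correctly formed weights built from baseline data alone leave 0.03 to 0.08 SD in scenarios like the last row. In the third and fourth rows they leave about 0.00 and −0.13 SD.

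**The case against.** A reader might infer that the plan has no missing-data handling for its primary endpoint. The documents do not support that. The SAP places its analyses under ITT, declares weighting and pattern mixture models for the ITT analysis, and includes the 2-month contrast in the GEE, a regression that the weights can enter. Pattern mixture models are not restricted to sleep outcomes. So the 2-month comparison is arguably covered by sensitivity analyses. What stands is that the named test is not modified, and that the scope over behavioural outcomes is ambiguous because the text sits in the sleep paragraph.

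A reader might also take Welch as the designated deciding analysis. The SAP ties it, and nothing else, to the words primary endpoint, but it describes the GEE as estimating the adjusted intervention effect and ranks neither. The supportable statement is that no deciding analysis is named.

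The bias depends on a one-sided loss pattern that was chosen, not documented, and it vanishes under two other reasonable patterns. That objection stands in full and limits the size claimed. It is also fair that moving from GEE to a likelihood model is partly a preference: a weighted GEE contrast named as deciding would close most of the gap within the existing plan.

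**Conclusion.** The point holds in a limited form. The only test tied to the 2-month primary endpoint is an available-case comparison that does not include everyone randomised. The SAP does not say how people without a 2-month score enter it, whether the missing-data methods extend to the behavioural outcomes, or which of two 2-month results decides.

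It would go too far to conclude that the trial's result will favour the app. The documents make unequal loss plausible but say nothing on the size or direction of outcome-related loss. Under the assumptions shown, and with no true effect, bias ranges from zero to about 0.25 SD towards the app, and false rejection from the nominal 5% to about 17%. At roughly 20% loss confined in its severity link to Group B, a more moderate reading is 0.12 to 0.19 SD and 7.5% to 11.9%. This should be corrected because the remedy is cheap, not because bias has been shown.

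**What to change.** In the first paragraph of the Statistical Analysis Plan, make the deciding 2-month analysis for each behavioural outcome the arm contrast at 2 months from one baseline-adjusted repeated-measures model (arm, visit as a factor, arm-by-visit) fitted to all available follow-up scores. A likelihood-based model is preferred because it lets 1-month scores inform those lost before the third visit.

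The planned GEE with correctly formed weights is an acceptable alternative, but it leaves some bias if the weights use baseline data only. The weights should be the inverse of the probability of being observed. The SAP's description refers to probabilities of dropout; taken literally, that gave −0.51 SD under no effect in the baseline-driven scenario (third row of the table).

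In the second paragraph, state that the weighting and pattern mixture analyses apply to this contrast, and say how they include participants with no follow-up score at all, whom the model alone does not reach. Keep Welch or Mann-Whitney as a labelled available-case check that does not decide the conclusion.

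The cost is SAP wording and a standard model. The downside is that the headline result rests on a model rather than a simple two-group test. The model reduces bias if data are missing at random; it does not remove it if dropouts lack a 1-month score or if loss depends on the unseen 2-month score.

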If the participant is randomized to Group A - They will be given a Fitbit Inspire to track the quality of their sleep and asked to download the Fitbit app to their smartphone. They will be provided with the information necessary to set up their account and instructed how to use the app to track their sleep. Please refer to the included script, *Fitbit Setup Guide* attachment, for more details. They will be asked to wear the Fitbit and record what time they went to bed & woke up in a sleep diary (which will be provided) for one week after the baseline visit, one week before the 3rd visit (in-person), and one week before the 4th visit (in-person). The total number of hours slept per night will be collected for the post-baseline period in Qualtrics via a personalized survey link while data will be collected in person for the other two use periods and recorded in Qualtrics. Upon completion of the third assessment, the UA app will be downloaded to his/her smartphone at no cost and with lifetime access. The participant will be instructed to watch the first module of the app and will review its features with the research team member to ensure they do not have any questions (see *UA Setup Guide* attachment for more details).

If the participant is randomized to Group B - They will be given a Fitbit and the process outlined above will be followed. In addition, the UA app will be downloaded to his/her smartphone and the same process will be followed as outlined above.

Both groups are expected to complete the following tasks / assessments at each research visit:

Baseline – In-person

- Group A will complete the first eight items using a personalized survey link (based on participant ID) via Qualtrics

- Group B will complete the first seven items using a personalized survey link via Qualtrics and the seventh, the GAD-7, will be completed as part of the Unwinding Anxiety assessment.
- Both groups will complete the shape matching task on a study laptop.
 1. Demographics. This form will be filled out in Qualtrics (age, gender, socioeconomic status, employment, education, race/ethnicity, relationship status) (approximately 3 minutes)

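### The change-score GEE does not name the outcome's own baseline value as a covariate, and does not say which contrast is the adjusted intervention effect although Group A gets the app after 2 months

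*Combined protocol and SAP*

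**What the plan says.** The Statistical Analysis Plan has two layers for the questionnaire outcomes. Welch's t-tests, or Mann-Whitney tests for non-normal data, examine "between-group differences in behavioral outcome measures at the primary endpoint (2 months"). A series of GEE models will then "estimate the adjusted intervention effect by regressing change in outcomes at each follow-up on time, group, time*group" and "confounders identified a priori (using correlation analysis"). The outcome's baseline value is not in that list of terms. It is named only in the weighting step for missing data, where "the probability of missingness is modeled as a function of baseline covariates and baseline values of the outcome". The coding of time is not given, and no coefficient or contrast is identified as the adjusted effect.

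For sleep the plan says: "Analysis will utilize the same approach as described for the behavioral measures".

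On timing, the third assessment is headed "Module 30 (Group B) or 2 Months (Group A") and the fourth "2 Months post-intervention (Group B) or 4 Months (Group A"). For Group A, Procedures states: "Upon completion of the third assessment, the UA app will be downloaded to his/her smartphone at no cost and with lifetime access".

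**The concern.** Two gaps sit in the same sentence of the plan.

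- **Covariate.** A change score without its baseline as covariate is less precise than the same model with it. Whether baseline enters depends on a correlation screen whose candidates, target and threshold are not stated. The plan aims for 64 usable data sets, so precision matters.
- **Contrast.** The GEE spans all follow-ups, but the last one comes after Group A has the app. The 4-month contrast is still randomized, but it compares immediate with delayed access, not app with usual care. Two analysts could follow the text and report different quantities under one label: a group term, an interaction, a 2-month difference, or a fitted value that borrows from month 4.

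**Working it through.** **Inputs.** From the documents: 64 complete data sets and 80 enrolled (Participant enrollment target), and the visit schedule and app access (Procedures). The documents give no alpha, power, effect size, SD, correlation or allocation ratio, so there is no planned power figure to reproduce. Assumed: 32 per arm, two-sided 5%, correlation r between baseline and follow-up of 0.3 to 0.7.

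**1. Baseline covariate, equal SDs at baseline and follow-up.** With follow-up SD 1, the residual SD is sqrt(2(1-r)) for change alone and sqrt(1-r^2) with the baseline covariate. The variance ratio is (1-r^2)/(2(1-r)) = (1+r)/2. Power is for a 0.5 SD effect (noncentral t, 62 and 61 df).

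| r | Variance ratio | Power, change alone | Power, with baseline | Detectable at 80% power (SD) |
|---|---|---|---|---|
| 0.3 | 0.65 | 38% | 54% | 0.84 to 0.68 |
| 0.5 | 0.75 | 50% | 62% | 0.71 to 0.62 |
| 0.7 | 0.85 | 72% | 79% | 0.55 to 0.51 |

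A test on raw follow-up scores has 50% power at every r.

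**2. Truncation of PSWQ and WIS.** Entry requires PSWQ above 40 and WIS of at least 5/10. Truncation shrinks the baseline SD more than the follow-up SD, so the equal-SD formula no longer applies. For a normal score cut at its mean (assumed), baseline variance is 1 - 2/pi = 0.363. Change variance is (1-r)^2 x 0.363 + (1-r^2), and adjusted variance is 1-r^2. At r = 0.5 before truncation: 0.25 x 0.363 + 0.75 = 0.841 against 0.75, a ratio of 0.89. At r = 0.6 and 0.7 the ratios are 0.92 and 0.94. Power for 0.5 of the follow-up SD goes from 50% to 55%, 54% to 58% and 60% to 63%. Selection acts on the screening score and the covariate would be the separate baseline-visit score, so the real restriction is indirect. These figures show the direction rather than a size for this trial.

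**3. What the correlation screen may already do.** Under equal SDs, baseline correlates with change at -sqrt((1-r)/2): -0.59, -0.50 and -0.39 at r = 0.3, 0.5 and 0.7. If baseline is a candidate and is tested against change at p < 0.05 (neither is stated), 20,000 simulated trials of 64 select it in over 99%, about 99% and about 90%. The gains in step 1 are therefore an upper bound.

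**4. Time coding.** Assume 0.70 SD at 2 months, r = 0.6 and visits at 1, 2 and 4 months. With linear time, the fitted month-2 value weights each visit by 1/3 + (2-7/3)(t-7/3)/(14/3), which gives 0.429, 0.357 and 0.214. Full catch-up by Group A after 2 months then removes 0.214 x 0.70 = 0.15 SD.

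| Effect at 1 month | Linear estimate: no, half, full catch-up | Power |
|---|---|---|
| 0.35 (ramp) | 0.55, 0.475, 0.40 | 84%, 72%, 57% |
| 0.70 (flat) | 0.70, 0.625, 0.55 | 96%, 92%, 84% |

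In the ramp case the straight-line misfit itself removes another 0.15 SD. Categorical visits give 0.70 throughout, with 87% power for change alone (SD 0.894, the basis of the linear figures too) and 93% with the baseline covariate (SD 0.80). Group B's visits follow modules rather than months, so its fitted value could differ from this calculation.

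**5. Baseline answered after allocation is known.** The envelope is opened before the baseline assessments. If this shifts one arm's baseline by s, the change score carries s, the adjusted contrast r x s, and a raw-score test 0. For s = 0.10 SD and no true effect, the bias is 0.10 for change and 0.03, 0.05, 0.07 adjusted (r = 0.3, 0.5, 0.7). Simulated false-positive rates are 6.0%, 6.7%, 8.2% for change, 5.0%, 5.5%, 6.6% adjusted, and about 4.7% raw.

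**6. Sleep outcomes.** The first Fitbit and diary week follows the baseline visit, at which Group B already receives the app. Change from that week, or adjustment for it, can remove part of the effect being measured.

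**The case against.** The strongest reply is that the plan is underspecified rather than wrong. Its wording refers to change at each follow-up, Group B's visits are defined by module, and the preceding sentence sets the primary endpoint at 2 months. Visit-specific effects are therefore the natural reading. The screen may also bring baseline in. This stands as a limit on size, but it settles neither point: the 2-month endpoint is attached to the unadjusted tests, and a screen is not a pre-specified covariate.

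Two further replies hold. A raw-score test avoids the baseline-shift problem altogether, and at r = 0.3 adjustment beats it by only 4 points (54% against 50%). Linear time can also have more power than unadjusted categorical visits when the effect is flat and Group A catches up little (96% or 92% against 87%). Linear time then buys power by changing what is estimated, and the comparison with the model recommended here is against 93%.

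A reader might infer three stronger points that the documents do not support:

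- **The primary comparison is contaminated by Group A's app use.** It is not: the 2-month test uses data collected before Group A has the app.
- **The change-score analysis is biased as such.** Under randomization it is unbiased in expectation. Bias arises only if knowing the allocation alters the baseline answers.
- **Truncation at entry makes the largest gain, at r = 0.3, likely for PSWQ and WIS.** Truncation lowers r but also shrinks the baseline SD, and step 2 shows that the net gain becomes smaller.

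**Conclusion.** The concern holds as a gap in the adjusted model only, of minor to moderate weight. The plan neither names the outcome's baseline value in the GEE nor defines the contrast that model is meant to deliver. For outcomes not truncated at entry, the possible gain is a variance factor of 0.65 to 0.85, or about 7 to 16 points of power at 0.5 SD. The full gain is lost only if the screen leaves baseline out. For PSWQ and WIS the worked case gives a factor of 0.89 to 0.94 and about 3 to 5 points. The cost of an open time coding is up to 0.15 SD of an assumed 0.70 SD effect through catch-up, and nothing if visits are categorical. All sizes rest on assumed correlations, effects and equal allocation. The direction of the precision result does not: in the equal-SD case (1+r)/2 is below 1 for every r below 1.

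**What to change.** 1. In the GEE for questionnaire outcomes, pre-specify the baseline-visit value of the same outcome as a covariate, in place of the correlation screen.
2. Code visit as categorical, name the group contrast at the third (2-month) assessment as the adjusted intervention effect, and report 4 months separately as immediate versus delayed access.
3. Keep the 2-month Welch or Mann-Whitney test, and state whether it uses raw or change scores.
4. For Fitbit and diary sleep, compare raw values at the 2-month wear period, with neither change from nor adjustment for the first wear week. The rule excluding participants who did not complete that first week would then need to be reconsidered, because the week no longer enters the comparison.

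**Cost.** SAP wording only, using scores already collected. One check is needed: Group B's baseline GAD-7 is taken inside the app's own assessment, so confirm that it precedes the first module. The downside is that the adjusted contrast carries r times any baseline shift caused by knowing the allocation. That is less than the planned change score carries but more than a raw-score test, which is a reason to report the adjusted contrast and a raw-score 2-month test side by side.
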